In the study, an observational clinical study strategy will be followed in routine spinal anesthesia applications. Applications will be made to the Erciyes University Ethics Committee. Patients will be informed before the procedure begins, and their written consent will be obtained. The study will be conducted from May 2025 to December 2025. ASA III and IV, preeclampsia, cardiorespiratory problems, pregnancy or pre-existing diabetes, intrauterine growth restriction, and fetal abnormalities, abruptio placentae, placenta previa, placenta accreta or percreta, pregnant women who are in an emergency situation and unwilling to participate, those with contraindications to spinal anesthesia, those weighing <50 kg or >110 kg, and those taller than 170 cm or shorter than 150 cm will not be included in the study. There was no pre-planning among the patients. The patient will undergo standard monitoring, including non-invasive blood pressure, ECG, and pulse oximetry, with baseline blood pressure and heart rate measurements recorded. Two 20-G intravenous cannulas will be inserted, and an IV balanced solution will be administered using these routes. Vertebral body length (VBL) measurements are determined by measuring from the midpoint of C7 to the Tuffier line. To test this hypothesis, a 0.5% heavy bupivacaine dose will be calculated as $0.2 \text{ mg} \times (\text{vertebral body length} = \text{distance between C7 and Tuffier's line}) \text{ cm}$. In our clinic, all three dose calculation systems are routinely used in spinal anesthesia for cesarean sections. As is routinely done, after skin infiltration with lidocaine, a 25-G short bevel Quincke spinal needle will be inserted into the L3-4 vertebral space while the patient is in a sitting position. After cerebrospinal fluid aspiration, the calculated dose of bupivacaine will be administered over 5 seconds. The patient and evaluator group assignments will be unknown. The data of 285 patients who underwent routine procedures will be examined, and the results will be separated based on the dose of bupivacaine administered to the pregnant woman. According to the results, the data is as follows: Patients in the VBU Group (thoracolumbar vertebral length between C7 and the Tuffier line) received $0.2 \text{ mg} \times \text{VBU cm}$ of 0.5% hyperbaric bupivacaine, while patients in the Height Group (calculated dose) received a volume of 0.5% hyperbaric bupivacaine based on a height-adjusted dose of 0.065 mg/cm height, calculated according to the patient's height. The AD Group (adjusted dosage) will receive intrathecal heavy bupivacaine (0.5%) as determined by Harten's dosage chart, adjusted for the patient's height and weight (Table 1) [11].

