The upper sensory level of anesthesia will be systematically assessed every two minutes along the midclavicular line using the loss of pinprick sensation. Additionally, the time to surgical incision, the sensory block level at the 30-minute mark, the application of Trendelenburg positioning, the administration of supplemental analgesia, and any transitions to general anesthesia will be recorded. Mean arterial pressure (MAP) and heart rate will be recorded at baseline and every 3 minutes thereafter, beginning 3 minutes after the spinal injection and continuing until the end of the surgical procedure. The occurrence of nausea and vomiting, along with the total amount of ephedrine administered, will be systematically documented. An attending nurse, blinded to the patients' group assignments, will assess Apgar scores at both 1 and 5 minutes post-delivery.

Statistical Analysis

A pre-study power analysis was performed using G*Power (v3.1.9.7; Franz Faul, Universität Kiel, Germany) based on the primary hypothesis defined as the rate of hypotension in each group. Using data from retrospective studies and assuming an effect size of 0.30, it was calculated that at least 69 patients per group (207 total) were required for an ANOVA test. This calculation provides a study power of 0.95 with a significance level (α) of 0.05.

Data will be analyzed using Analysis of Variance (ANOVA), the Kruskal-Wallis test, and Fisher's exact test, as appropriate. Bonferroni corrections will be applied for multiple comparisons. A p-value < 0.05 will be considered statistically significant. All statistical analyses will be performed using JAMOV version 2.6.19 for Windows.

References:

- 3-Šklebar I, Bujas T, Habek D. Spinal anaesthesia-induced hypotension in obstetrics: Prevention and therapy. *Acta Clin Croat* 2019;58(Suppl 1):90-5.

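### The stated power of 0.95 is for the overall three-group test only; no pairwise power is given, and for three groups a closed test identifies which groups differ with more power than Bonferroni at the same familywise error

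*Combined protocol and SAP*

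**What the plan says.** The opening description of the design defines three groups by how the bupivacaine dose was calculated: vertebral length, height, or height and weight by chart. It states that 285 patients' data will be examined and does not fix the group sizes.

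The Statistical Analysis section describes the power calculation as "based on the primary hypothesis defined as the rate of hypotension in each group". It proceeds by "assuming an effect size of 0.30" and concludes that "at least 69 patients per group (207 total) were required for an ANOVA test". It adds: "This calculation provides a study power of 0.95 with a significance level (α) of 0.05".

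For the analysis: "Data will be analyzed using Analysis of Variance (ANOVA), the Kruskal-Wallis test, and Fisher's exact test, as appropriate". On multiplicity there is one sentence: "Bonferroni corrections will be applied for multiple comparisons". The section names no primary pairwise contrast, does not say whether the correction covers pairs of groups, several outcomes or both, and mentions no closed or stepwise procedure.

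**The concern.** A significant overall test says that the three hypotension rates are not all equal. It does not say which dosing method differs from which. That takes pairwise tests, and Bonferroni is the only follow-up the plan names. If the family is the three pairs, each test is run at 0.0167, whereas the sample size used an undivided 0.05. A reader who takes 0.95 as the chance of separating one method from another would be relying on a figure the plan never calculated.

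Three groups is also a special case in which the pairwise tests need no further division of alpha once the overall test is significant. At stake is some power to identify which groups differ, recoverable without more patients or data.

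**Working it through.** **Inputs from the plan.** Three groups; effect size 0.30 (read as Cohen's f because the test is ANOVA; the metric is not named); alpha 0.05; power 0.95; 69 per group, 207 in total; 285 patients examined, which is 285/3 = 95 per group if the groups are equal.

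**Assumptions.** The plan gives no hypotension rates and no group sizes, so all rates below and the equal groups are assumed.

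**1. The plan's own figure.** For one-way ANOVA the noncentrality is N × f². At N = 207 it is 207 × 0.09 = 18.63, and with 2 and 204 degrees of freedom the overall power is 0.977. Power 0.95 needs 59 per group (177 in total). The 69 is therefore not reproduced from the stated inputs, but the difference is on the safe side. At 285 patients the overall power is 0.997. The stated 0.95 is not too high for the overall test.

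**2. Why the closed test is valid here.** The pairwise nulls are A = B, A = C and B = C. Any two of them imply A = B = C, so the only intersection hypothesis is the global null. Closed testing requires a 0.05 test of the global null and a 0.05 test of each pair. An overall test at 0.05 followed, if significant, by each pair at 0.05 does exactly that, and controls the familywise error strongly. This does not extend to more than three groups.

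**3. Matching rates to the planning effect.** f = √(between-group variance of the rates / mean within-group variance).
- 50/50/20%: mean 0.40; between = (0.01 + 0.01 + 0.04)/3 = 0.02; within = (0.25 + 0.25 + 0.16)/3 = 0.22; f = √(0.02/0.22) = 0.30. This is the planning effect.
- 50/50/30%: mean 0.433; between = 0.0089; within = (0.25 + 0.25 + 0.21)/3 = 0.2367; f = 0.19. This is well below the planning effect.

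**4. Simulated power** (200,000 studies per scenario; chi-square overall test, pooled z pairwise tests; the two true pairs are the odd group against each other group). Each cell is Bonferroni → closed.

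| Assumed rates | n per group | Each true pair | Both true pairs |
|---|---|---|---|
| 50/50/20% | 69 | 0.92 → 0.96 | 0.86 → 0.94 |
| 50/50/20% | 95 | 0.98 → 0.99 | 0.96 → 0.99 |
| 50/50/30% | 69 | 0.52 → 0.60 | 0.35 → 0.51 |
| 50/50/30% | 95 | 0.66 → 0.77 | 0.51 → 0.69 |

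At 50/50/20% and 69 per group, the power to find at least one true difference is 0.977 → 0.981.

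**5. Familywise error.** With all rates at 40%, the closed test rejects at least one pair in 0.050 (69 per group) and 0.049 (95 per group) of studies. When one pair is truly equal and the third group differs, the closed test rejects that pair at about 0.05; Bonferroni does so at 0.015 to 0.017.

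**6. Separating the causes at 50/50/30%, 69 per group.** The overall test itself has power 0.70. Of the gap 0.95 − 0.52 = 0.43, dropping Bonferroni recovers only 0.60 − 0.52 = 0.08. The rest does not come from Bonferroni, and most of it comes from the smaller effect.

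**7. Sensitivity to test and pattern (f = 0.30).** With Fisher's exact pairwise tests at rates of 39/39/71% and 69 per group, each true pair goes from 0.904 to 0.953. With three equally spaced means at 69 per group, adjacent pairs go from 0.402 to 0.575 and the extreme pair only from 0.971 to 0.976. At 95 per group the adjacent pairs go from 0.551 to 0.715.

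**The case against.** Bonferroni is valid, and the plan ties its power figure explicitly to an ANOVA. Replacing one valid method by a more powerful one is refinement. At the planning effect with 285 patients in equal groups, Bonferroni already gives 0.98 per comparison and 0.96 for both when one group differs. All of this stands, and it limits the size of the point.

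The family is also undefined. If the correction is meant to cover several outcomes, it does work that a closed test across three groups does not do. That stands too, and is a reason to have the plan name the family.

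The closed test does not beat Bonferroni in every data set. At 50/50/30% with 69 per group, about 1% of simulated studies lose a rejection that Bonferroni would have made, because the overall test is not significant. The plain 95% confidence intervals are not simultaneous. Both are real but small costs.

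Three stronger readings are tempting and not supported:
- A reader might infer that the stated 0.95 is wrong. For the overall test it is not; 207 patients give 0.977.
- A reader might infer from the figures near 0.5 that Bonferroni badly underpowers the study. Those figures assume an effect of about 0.19 in place of the planned 0.30, and most of the shortfall comes from that.
- A reader might infer that the primary claim is vertebral-length dosing against each other method. The Statistical Analysis section speaks only of the hypotension rate in each group.

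**Conclusion.** The point holds as an inexpensive improvement. The plan gives power for the overall three-group test and none for the comparisons that would show which method differs. If Bonferroni is applied to the three pairs, it is stricter than it needs to be once the overall test is significant.

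At the planning effect and 69 per group, the closed test adds about 4 points per true comparison and 8 points for both. At 95 per group it adds about 1 and 3 points. At the smaller assumed effect it adds 8 to 11 points per comparison and 16 to 18 for both. The benefit lies in identifying which pairs differ; the chance of finding at least one true difference hardly moves at the planning effect.

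These sizes rest on assumed rates, equal groups, reading 0.30 as Cohen's f, and chi-square and pooled z tests. The validity of the closed test does not depend on the assumed rates, provided each component test holds its level.

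**What to change.** In the Statistical Analysis section, for the primary hypotension endpoint:
- Test the three groups with an overall 3×2 test (chi-square or Fisher-Freeman-Halton) at 0.05. If it is significant, test the three pairs each at 0.05, and describe this as a closed procedure with familywise error 0.05.
- State that the 0.95 refers to the overall test, and give the pairwise power with the hypotension rates assumed for it.
- Say which comparisons form the family for any Bonferroni correction, and keep Bonferroni for families of more than three comparisons.
- Report pairwise risk differences with 95% confidence intervals, noting that they are not simultaneous.

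The cost is a few sentences, with no extra patients, data or change to care. The price is that no pairwise claim can be made unless the overall test is significant.
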